5.5 Withdrawal of Subjects and Discontinuation of Study

A subject may voluntarily withdraw or be withdrawn from the study at any time for reasons including, but not limited to, the following:

- clinically significant abnormal laboratory results or AEs, which rule out continuation of the study drug, as determined by the investigator or the AbbVie TA MD;
- investigator's opinion that discontinuation is in the best interest of the subject;
- subject requests withdrawal from the study;
- eligibility criteria violation was noted after the subject started study drug and continuation of the study drug would place the subject at risk;
- introduction of prohibited medications or dosages and continuation of the study drug would place the subject at risk;
- subject becomes pregnant while on study drug;
- subject is significantly noncompliant with study procedures which would put the subject at risk for continued participation in the trial.

Each subject must be withdrawn if any of the following occur:

- disease progression confirmed with IMWG criteria
- drug-related toxicities that lead to dose interruption of > 28 days (subjects may remain in the study if only 1 treatment is discontinued)
- use of antimyeloma treatment not specified in the protocol or operations manual and before documented disease progression

For subjects to be considered lost to follow-up, reasonable attempts must be made to obtain information on the final status of the subject. At a minimum, 2 telephone calls must be made and 1 certified letter must be sent and documented in the subject's source documentation.

AbbVie may terminate this study prematurely, either in its entirety or at any site. The investigator may also stop the study at his/her site if he/she has safety concerns. If AbbVie terminates the study for safety reasons, AbbVie will promptly notify the investigator.

In the event a subject withdraws consent to participate in the clinical study and AbbVie is notified in writing, no new biomarker data will be collected from the withdrawn subject or added to the existing data or database(s). A subject may withdraw consent for optional research at any time and remain in the clinical study. Data generated from biomarker research samples collected before subject withdrawal of consent will remain part of the study results.

5.6 Follow-Up for Subject Withdrawal from Study

To minimize missing data for efficacy and safety assessments, subjects who prematurely discontinue study drug treatment should continue to be followed for all regularly scheduled visits, unless subjects have decided to discontinue the study participation entirely (withdrawal of informed consent). Subjects should be advised on the continued scientific importance of their data even if they discontinue treatment early.

If a subject discontinues study participation (withdrawal of informed consent), the procedures outlined for the end-of-treatment visit should be completed as soon as possible, preferably within 2 weeks. In addition, if subject is willing, a 30-day follow-up phone call after the last dose of study drug may be completed to ensure all treatment-emergent AEs/SAEs have been resolved to a \leq Grade 1 or baseline level or, in the opinion of the investigator, the event is unlikely to resolve.

All attempts must be made to determine the date of the last study drug dose and the primary reason for the discontinuation of the study drugs or study participation. The information will be recorded on the appropriate eCRF page. However, these procedures should not interfere with the initiation of any new treatments or therapeutic modalities that the investigator feels are necessary to treat the subject's condition. Following the discontinuation of the study drugs, the subject will be treated in accordance with the investigator's clinical judgment, irrespective of whether or not the subject decides to continue participation in the study.

5.7 Study Drugs

Venetoclax manufactured by AbbVie will be administered PO, QD for each 28-day cycle beginning on Day 1 and should be taken at approximately the same time each day. Subjects will be trained to self-administer venetoclax (refer to Operations Manual Section 4.1).

Pomalidomide will be administered PO, QD on Days 1 to 21 for each repeated 28-day cycle. Subjects will be trained to self-administer pomalidomide (refer to Operations Manual Section 4.1).

Subject dosing will be recorded in a subject dosing diary. The subject will be instructed to return all drug containers (even if empty) to the study site personnel at each study visit. The study site personnel will document compliance.

AbbVie will not supply drugs other than venetoclax and pomalidomide, if applicable. Dexamethasone and any other noninvestigational medicinal products (standard of care) must be obtained commercially.

Pomalidomide will be dispensed as noninvestigational medical product in the US under the Pomalyst REMS program. Further information can be found at: www.CelgeneRiskManagement.com.

Study drug information is presented in [Table 2](#).

Table 2. Study Drug Information

Investigational Product	Manufacturer	Mode of Administration	Dosage Form	Strength
Venetoclax	AbbVie	Oral	Film-coated tablet	100 mg
Pomalidomide	Celgene	Oral	Capsules	1, 3, and/or 4 mg

Venetoclax will be packaged in bottles with quantities sufficient to accommodate study design. Pomalidomide will be packaged in bottles or blisters in cartons (local marketed product or overlabeled product with a clinical study label). Each kit will be labeled per local requirements and this label must remain affixed to the kit. Upon receipt, study drugs should be stored as specified on the label and kept in a secure location. Each kit will contain a unique kit number. This kit number is assigned to a subject via Interactive Response Technology (IRT) and encodes the appropriate study drugs to be dispensed at the subject's corresponding study visit. Study drugs must not be dispensed without contacting the IRT system. Study drugs will only be used for the conduct of this study.

Information on the investigational products is provided in Operations Manual Section 4.

5.8 Randomization/Drug Assignment

This is an open-label study. There is no randomization for this study. All subjects will be assigned a unique identification number by the IRT at the screening visit following signed consent and completion of at least 1 study-required procedure. For subjects who rescreen, the screening number assigned by the IRT at the initial screening visit should be used.

5.9 Protocol Deviations

The investigator is responsible for complying with all protocol requirements, written instructions, and applicable laws regarding protocol deviations. Protocol deviations are prohibited except when necessary to eliminate an immediate hazard to study subjects. If a protocol deviation occurs (or is identified), the investigator is responsible for notifying IEC/IRB, regulatory authorities (as applicable), and AbbVie.

6 SAFETY CONSIDERATIONS

6.1 Complaints and Adverse Events

Complaints

A complaint is any written, electronic, or oral communication that alleges deficiencies related to the physical characteristics, identity, quality, purity, potency, durability, reliability, safety, effectiveness, or performance of a product. Complaints associated with any component of this investigational product must be reported to AbbVie.

Medical Complaints/Adverse Events and Serious Adverse Events

An AE is defined as any untoward medical occurrence in a subject or clinical investigation subject administered a pharmaceutical product and which does not necessarily have a causal relationship with this treatment. An AE can therefore be any unfavorable and unintended sign (including an abnormal laboratory finding), symptom, or disease temporally associated with the use of a medicinal (investigational) product, whether or not the event is considered causally related to the use of the product.

An AE can result from use of the drug as stipulated in the protocol or labeling, as well as from accidental or intentional overdose, drug abuse, or drug withdrawal. Any worsening of a pre-existing condition or illness is considered an AE. Worsening in severity of an AE should be reported as a new AE. Laboratory abnormalities and changes in vital signs are considered to be AEs only if they result in discontinuation from the study, necessitate therapeutic medical intervention, meet protocol-specified criteria (see Section 6.4 regarding toxicity management), and/or if the investigator considers them to be AEs.

The investigators will monitor each subject for clinical and laboratory evidence of AEs on a routine basis throughout the study. The investigator will assess and record any AE in detail including the date of onset, event diagnosis (if known), or sign/symptom, severity, time course (end date, ongoing, intermittent), relationship of the AE to study drug, and any action(s) taken. For SAEs considered as having "no reasonable possibility" of being associated with study drug, the investigator will assign "other" as the cause of the event. For AEs to be considered intermittent, the events must be of similar nature and severity. AEs, whether in response to a query, observed by site personnel, or reported spontaneously by the subject, will be recorded.

All AEs will be followed to a satisfactory conclusion.

An elective surgery/procedure scheduled to occur during a study will not be considered an AE if the surgery/procedure is being performed for a pre-existing condition and the surgery/procedure was preplanned before study entry. However, if the pre-existing condition deteriorates unexpectedly during the study (e.g., surgery performed earlier than planned) then the deterioration of the condition for which the elective surgery/procedure being done will be considered an AE.

[figure not shown]
If an AE meets any of the following criteria, it is to be reported to AbbVie or contract research organization (as appropriate) as an SAE within 24 hours of the site being made aware of the SAE:

Death of Subject	An event that results in the death of a subject.
Life Threatening	An event that, in the opinion of the investigator, would have resulted in immediate fatality if medical intervention had not been taken. This does not include an event that would have been fatal if it had occurred in a more severe form.
Hospitalization or Prolongation of Hospitalization	An event that results in an admission to the hospital for any length of time or prolongs the subject's hospital stay. This does not include an emergency room visit or admission to an outpatient facility.
Congenital Anomaly	An anomaly detected at or after birth or any anomaly that results in fetal loss.
Persistent or Significant Disability/Incapacity	An event that results in a condition that substantially interferes with the activities of daily living of a subject. Disability is not intended to include experiences of relatively minor medical significance such as headache, nausea, vomiting, diarrhea, influenza, and accidental trauma (e.g., sprained ankle).
Important Medical Event Requiring Medical or Surgical Intervention to Prevent Serious Outcome	An important medical event that may not be immediately life-threatening or result in death or hospitalization but, based on medical judgment, may jeopardize the subject and may require medical or surgical intervention to prevent any of the outcomes listed above (i.e., death of subject, life threatening, hospitalization, prolongation of hospitalization, congenital anomaly, or persistent or significant disability/incapacity). Additionally, any elective or spontaneous abortion or stillbirth is considered an important medical event. Examples of such events include allergic bronchospasm requiring intensive treatment in an emergency room or at home, blood dyscrasias or convulsions that do not result in inpatient hospitalization, or the development of drug dependency or drug abuse.

Hospitalization of a subject to allow observation and management (e.g., intravenous [IV] hydration) for the purpose of TLS prophylaxis will not be captured as an SAE unless there is an additional reason for hospitalization or an additional criterion for seriousness other than hospitalization (e.g., abnormal postdose TLS laboratories that necessitate therapeutic medical intervention, etc.).

All AEs reported from the time the study drugs are administered until 30 days after discontinuation of any study drug will be collected whether solicited or spontaneously reported by the subject. In addition, protocol-related SAEs and nonserious AEs will be collected from the time the subject signed the study-specific informed consent.

All AEs should be followed until resolution, return to baseline, or determined to be stable per the investigator.

AE = adverse event; SAE = serious adverse event

* Only if considered by the investigator to be causally related to study-required procedures.

a. 30 Days after the last dose of venetoclax.

Adverse Event Severity and Relationship to the Study Drugs

The investigators will rate the severity of each AE according to the National Cancer Institute (NCI) Common Terminology Criteria for Adverse Events (CTCAE) version 4.03. If a reported AE increases in severity, the initial AE should be given an outcome date and a new AE must be reported on a different onset date than the end date of the previous AE to reflect the change in severity. The dates on the AEs cannot overlap. For all reported SAEs that increase in severity, the supplemental eCRFs also need to be updated to reflect any changes due to the increase in severity.

For AEs not captured by the NCI CTCAE, the following should be used:

- Grade 1** The AE is transient and easily tolerated by the subject (mild).
- Grade 2** The AE causes the subject discomfort and interrupts the subject's usual activities (moderate).
- Grade 3** The AE causes considerable interference with the subject's usual activities and may be incapacitating (moderate to severe).
- Grade 4** The AE is life-threatening and requires urgent intervention (severe).
- Grade 5** The AE resulted in death of the subject (severe).

The investigators will use the following definition to assess the relationship of each AE to the use of the study drugs:

Reasonable Possibility	After consideration of factors including timing of the event, biologic plausibility, clinical judgment, and potential alternative causes, there is sufficient evidence (information) to suggest a causal relationship.
No Reasonable Possibility	After consideration of factors including timing of the event, biologic plausibility, clinical judgment, and potential alternative causes, there is no evidence (information) to suggest a causal relationship.

For causality assessments, events assessed as having a reasonable possibility of being related to the study drug will be considered "associated." Events assessed as having no reasonable possibility of being related to study drug will be considered "not associated." In addition, when the investigator has not reported causality or deemed it not assessable, AbbVie will consider the event associated.

If an SAE is assessed as having no reasonable possibility of being related to study drug per the investigator's opinion, an "other" cause of event must be provided by the investigator for the SAE.

Adverse Events of Special Interest

AEs will be monitored throughout the study to identify any of special interest that may indicate a trend or risk to subjects. The following AEs of special interest (serious and nonserious) are to be entered into the electronic data capture system immediately (i.e., no more than 24 hours after the site becoming aware of the event):

- TLS

Dose-Limiting Toxicity

DLTs (as defined Section 6.5) will be assessed during the first cycle of venetoclax and pomalidomide dosing. Toxicities occurring after the first cycle of dosing will also be evaluated by the investigator and the AbbVie TA MD and taken into consideration for dose-escalation decisions.

Pregnancy

While not an AE, pregnancy in a study subject must be reported to AbbVie within 1 working day of the site becoming aware of the pregnancy. If a pregnancy occurs in a study subject or in the partner of a study subject, information regarding the pregnancy and the outcome will be collected. In the event of pregnancy occurring in a subject's partner during the study, written informed consent from the partner must be obtained before collection of any such information. A separate consent will be provided by AbbVie for this purpose. Pregnancies in study subject's partners will be collected from the date of the first dose through 30 days following the last dose of study drug.

The pregnancy outcome of an elective or spontaneous abortion, stillbirth, or congenital anomaly is considered an SAE and must be reported to AbbVie within 24 hours of the site becoming aware of the event.

Deaths

Deaths that occur during the protocol-specified AE reporting period that are attributed by the investigator solely to progression of MM should be recorded only on the study completion eCRF with

disease progression as the reason for discontinuation and not on the AE eCRF. All other on-study deaths, regardless of relationship to study drug, must be recorded on the AE eCRF and immediately reported to the sponsor.

Death should be considered an outcome and not a distinct event. The event or condition that caused or contributed to the fatal outcome should be recorded as the single medical concept on the AE eCRF. Generally, only 1 such event should be reported. The term "sudden death" should be used only for the occurrence of an abrupt and unexpected death because of presumed cardiac causes in a subject with or without pre-existing heart disease within 1 hour after the onset of acute symptoms or, in the case of an unwitnessed death, within 24 hours after the subject was last seen alive and stable. If the cause of death is unknown and cannot be ascertained at the time of reporting, "unexplained death" should be recorded on the AE eCRF. If the cause of death later becomes available (e.g., after autopsy), "unexplained death" should be replaced by the established cause of death.

Lack of Efficacy or Worsening of Disease

Events that are clearly consistent with the expected pattern of progression of the underlying disease, including transformation to a more aggressive histology, are also considered an expected outcome for this study and will NOT be recorded as AEs. These data will be captured as efficacy assessment data only. If there is any uncertainty as to whether an event is due to disease progression, the event should be reported as an AE.

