3 STUDY OBJECTIVES AND ENDPOINTS

3.1 Objectives

Primary

The primary objective of this study is:

- To characterize the safety and tolerability profiles of venetoclax combined with pomalidomide and dexamethasone when co-administered in subjects with R/R MM

Secondary

The secondary objectives of this study are:

- To evaluate the anti-MM activity of co-administered venetoclax combined with pomalidomide and dexamethasone therapy
- To characterize the plasma pharmacokinetics (PK) of venetoclax and pomalidomide when co-administered in subjects with R/R MM

Exploratory

The exploratory objectives of this study are:

- To evaluate correlative biomarkers of co-administered venetoclax combined with pomalidomide and dexamethasone therapy including, but not limited to, BCL-2 family member expression and chromosomal abnormalities
- To assess minimal residual disease (MRD) negativity in the bone marrow by next generation sequencing

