- platelets $\geq 50,000/\text{mm}^3$
- all other AEs should resolve to \leq Grade 2

Subjects will receive venetoclax and pomalidomide until documented disease progression, documented unacceptable toxicity, withdrawal of consent, or the subject meets other criteria for discontinuation per study protocol (Section 5.5). Subjects will remain on study treatment as long as venetoclax or pomalidomide/dexamethasone is being administered. Subjects may discontinue pomalidomide/dexamethasone but may continue receiving venetoclax QD as monotherapy for up to 2 years following the date of the last subject enrolled on study provided the subject completed venetoclax plus pomalidomide and dexamethasone dosing in Cycle 1, continue to tolerate venetoclax, have no evidence of disease progression, and do not meet any criteria for treatment discontinuation. For subjects that

continue to derive benefit after 2 years of treatment following the date of the last subject enrolled, AbbVie will work with the investigator to evaluate options for continuation of venetoclax therapy.

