The AbbVie Therapeutic Area Medical Director (TA MD) identified in [Appendix L](#) should be contacted if there are any questions regarding concomitant or prior therapy(ies) and venetoclax or pomalidomide dose reductions.

Table 9. Study Drug Dose Levels

Dose	Venetoclax	Pomalidomide	Dexamethasone (< 75 years of age)	Dexamethasone (≥ 75 years of age)
Starting dose	800 mg	4 mg	40 mg	20 mg
Dose level –1	600 mg	3 mg	20 mg	12 mg
Dose level –2	400 mg	2 mg	12 mg	8 mg
Dose level –3	200 mg	1 mg	8 mg	4 mg

Table 10. Toxicities Related to Venetoclax

Toxicities	Recommended Action
Grade 3 or Grade 4 neutropenia with infection or fever; or Grade 4 hematologic toxicities (except for lymphopenia)	
 • G-CSF or growth factors for neutropenia should be administered with venetoclax if clinically indicated. • For Grade 4 neutropenia (ANC < 500 cells/μL) without infection, anti-infective prophylaxis (e.g., amoxicillin/clavulanic acid or levofloxacin or equivalent per institutional guidelines) is recommended until the neutropenia improves to Grade 3 or better (ANC > 500 cells/μL). • First episode: Interrupt venetoclax and once the toxicity has resolved to Grade 1 or baseline level, venetoclax may be resumed at the same dose. • For subsequent episodes: Interrupt venetoclax. Consider using G-CSF as clinically indicated. Follow dose reduction guidelines when resuming treatment with venetoclax after resolution. A larger dose reduction may occur at the discretion of the investigator and according to the dose reduction guidelines.
Grade \geq 3 or serious infections	
 • Interrupt venetoclax and upon resolution, treatment can either be resumed at a reduced dose (see Table 9) or discontinued, at the discretion of the investigator.
Grade 3 or 4 non-hematologic events	
 • First episode: Interrupt venetoclax. Once toxicity has resolved to Grade \leq 1 or baseline, venetoclax may be resumed at the same dose. No dose modification is required. • For subsequent episodes: Interrupt venetoclax. Follow dose reduction guidelines when resuming treatment with venetoclax after resolution. A larger dose reduction may occur at the discretion of the investigator and according to the dose reduction guidelines.

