## **7.0 Safety Analyses**

### **7.1 Analysis of Adverse Events**

AE analysis will only include treatment-emergent events (those that have an onset on or after the day of the first dose of any study drug), and will not include AEs that have an onset of more than 30 days after the last dose of any study drug.

Treatment-emergent AEs will be coded and summarized by system organ class and preferred term according to the Medical Dictionary for Regulatory Activities (MedDRA) AE coding dictionary. The percentage of subjects experiencing an AE at a given severity will be provided along with the NCI CTCAE version 4.03 toxicity grade and relationship to the study drugs. Serious AEs, AEs leading to discontinuation of treatment, and AEs leading to death will be summarized. All summaries will be done by dose. For the study as a whole, AEs will be evaluated and summarized.

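### Protocol Section 6.1 gives two different ends to adverse event collection, and they diverge when venetoclax is stopped before pomalidomide/dexamethasone

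*Protocol*

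**What the plan says.** **When collection ends.** The body of Protocol Section 6.1 says that AEs arising from first administration of the study drugs "until 30 days after discontinuation of any study drug will be collected". A few lines later, below a key that defines only AE and SAE, footnote a says: "30 Days after the last dose of venetoclax". The figure that these notes accompany is not visible in the copy reviewed.

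**What is analysed.** SAP 7.1 starts counting events at first dosing. At the other end, the analysis "will not include AEs that have an onset of more than 30 days after the last dose of any study drug".

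**Whether venetoclax can stop first.** Protocol Section 4.1 says: "Subjects will remain on study treatment as long as venetoclax or pomalidomide/dexamethasone is being administered". Section 5.5, on toxicity-related interruptions beyond 28 days, adds that "subjects may remain in the study if only 1 treatment is discontinued". Appendix I, Table 10 gives one concrete route: after a Grade 3 or higher, or serious, infection, venetoclax may be restarted at a reduced dose "or discontinued, at the discretion of the investigator".

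**Why the window matters.** The primary objective in Protocol Section 3.1 is "To characterize the safety and tolerability profiles of venetoclax combined with pomalidomide and dexamethasone when co-administered in subjects with R/R MM".

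**The concern.** One section gives sites two written cut-offs for the same activity. They coincide in some subjects and differ in others, and the protocol permits the order of stopping in which they differ. A subject who comes off venetoclax after a serious infection and continues pomalidomide/dexamethasone is still on study treatment by the protocol's own definition, yet the footnote would close AE recording 30 days after the last venetoclax dose.

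The body text does not settle the matter, because its wording can be taken as the first study drug stopped or the last. The first-stopped reading would also end recording during treatment.

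At stake is the completeness and uniformity of the data behind the primary objective. Sites applying different rules would return different records for similar subjects. An event that was never entered cannot be restored at analysis, however SAP 7.1 is read.

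**Working it through.** The plan states no figure to reproduce. The check sets the end points side by side and works out when they differ.

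**Notation.** V is the day of the last venetoclax dose. F is the day of the last dose of whichever drug stops first, and L the same for whichever stops last.

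| Source | End of window |
|---|---|
| Protocol 6.1, footnote a | V + 30 |
| Protocol 6.1, text, read as last drug stopped | L + 30 |
| Protocol 6.1, text, read as first drug stopped | F + 30 |
| SAP 7.1, ordinary reading | L + 30 |
| Protocol Appendix D, safety follow-up note | about L + 30, or before subsequent treatment if sooner |

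**Case 1: venetoclax stops last (V = L).** The footnote gives L + 30, so its gap against SAP 7.1 is (L + 30) − (V + 30) = 0. This covers the venetoclax monotherapy route described in Section 4.1. The first-stopped reading of the text would still close collection L − F days early here.

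**Case 2: venetoclax stops first (V = F, earlier than L).** The footnote and the first-stopped reading both give V + 30. The gap is (L + 30) − (V + 30) = L − V, the number of days on pomalidomide/dexamethasone after venetoclax. Of these, max(0, L − V − 30) days fall while the subject is still on treatment. The remaining min(30, L − V) fall after the last dose.

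**Illustration of Case 2.** The documents give no duration of pomalidomide/dexamethasone after venetoclax, so the number of further 28-day cycles, k, is an assumption. Taking L − V as about 28k days:

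| k | Gap, 28k (days) | Of which on treatment, max(0, 28k − 30) | Of which after last dose |
|---|---|---|---|
| 1 | 28 | 0 | 28 |
| 3 | 84 | 54 | 30 |
| 6 | 168 | 138 | 30 |
| 12 | 336 | 306 | 30 |

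These are days of follow-up for one such subject at a site that applied the footnote literally. They are not counts of lost events.

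**What footnote a marks.** The asterisked note beside it limits certain events to those caused by study-required procedures. That matches the Section 6.1 sentence on protocol-related events collected from consent, at the start of the timeline. The natural counterpart for footnote a is the end of the same timeline. This is an inference, which a reader with the figure can confirm.

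**Which drugs count.** Protocol Section 5.7, Table 2 lists only venetoclax and pomalidomide, and the same section places dexamethasone with the noninvestigational products. Appendix I, Table 9, whose title refers to study drug dose levels, includes dexamethasone. L itself is therefore not fully defined.

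**The case against.** The strongest reply is that the rest of the protocol already requires collection from these subjects:

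- Appendix D marks AE assessment across the treatment visits, at end of treatment and at safety follow-up.
- The Appendix D note ties safety follow-up to the last dose of study drug, not of venetoclax.
- Section 6.1 asks investigators to monitor for AEs routinely throughout the study, and Section 3.4 frames safety evaluation over the whole study.
- Section 5.6 keeps subjects who stop study drug early on the visit schedule.
- Section 6.1 sends every on-study death not attributed solely to myeloma progression to the AE form.

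A site would have to put one footnote above all of these. This stands, and it is why loss is only possible; for deaths, the separate recording rule gives further protection. It does not remove the conflict. It shows the footnote to be the outlier.

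Two further replies also have force. The figure cannot be seen, so the footnote's anchor is inferred. And the single-drug route that Section 4.1 spells out is venetoclax alone, where the footnote causes no gap. Sections 4.1 and 5.5 nevertheless allow the reverse order, and Table 10 gives a reason for it.

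It can also be said that SAP 7.1 has an ordinary meaning, the last dose of whichever drug is taken last. That is fair: the SAP needs at most a matching phrase, and the conflict lies in the protocol.

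**Conclusion.** Section 6.1 contradicts itself on when AE collection ends, and should be corrected. The contradiction takes effect under the footnote when venetoclax stops before pomalidomide/dexamethasone, and under a first-stopped reading of the text whenever the drugs stop at different times. Events could then go unrecorded during study treatment and be missing from the SAP 7.1 summary.

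The size cannot be estimated from the documents, which give neither the proportion stopping venetoclax first nor the time on the other drugs afterwards. The footnote's effect is zero if no subject stops venetoclax first, or if every site follows the schedule. The conclusion assumes that footnote a marks the end of the AE timeline.

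Three stronger readings are tempting and are not supported:

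- **That AEs will be lost, in some number of subject-months.** This needs an invented stopping rate and duration, and assumes that every site follows the footnote against the schedule.
- **That the combination will look safer than it is.** The direction of bias is not shown. The objective concerns the drugs when given together, and events more than 30 days after venetoclax, on pomalidomide/dexamethasone alone, say less about that.
- **That a primary safety analysis is compromised.** The documents name no such analysis. The link is to the primary objective and the treatment-emergent AE summary.

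Nor does anything suggest that a venetoclax-only window was a deliberate choice. It reads as an inconsistency.

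**What to change.** Reconcile footnote a and the Section 6.1 text with the Appendix D safety follow-up note and SAP 7.1, using one explicit end point. For example: AEs are collected through 30 days after the last dose of whichever study drug is stopped last. State beside it which drugs count as study drug for this window, and in particular whether dexamethasone does. Carry the same phrase into SAP 7.1 so that the collection and analysis windows match. The Section 6.1 rule on deaths refers to the AE reporting period, so it will take the same definition without further change.

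The cost is wording only. AEs are collected at visits already scheduled; no visit is added and no treatment rule changes.
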